6.1 Information to be collected on screening failures

All subjects who have signed informed consent but do not enter the next period (i.e. Randomized treatment to Month 12) will have the study completion CRF for the screening period, demographics (giving reason for screen failure), inclusion/exclusion and SAE data collected. Adverse events that are not SAEs will be followed by the investigator and collected only in the source data. All consented subjects must be entered in the interactive response technology (IRT) system at screening. For subjects who are not randomized the IRT and Screening Disposition CRF must both be updated to indicate screen failure.

Rescreening is only allowed for subjects who were screen failures on the initial Screening visit e.g. due to lab values out of range. Rescreened subjects should be recorded as screen failures under their original Subject ID number and assigned a new Subject ID number in the Database when consented for rescreening.

All subjects who have signed informed consent and enter the next period of the study (i.e. are randomized to treatment) will have all adverse events occurring after informed consent is signed recorded on the Adverse Event CRF.

Investigators will have the discretion to record abnormal test findings on the medical history CRF whenever in their judgment, the test abnormality occurred prior to the informed consent signature.

6.2 Subject demographics/other baseline characteristics

After informed consent has been signed and the subject's eligibility to participate in the study has been determined, baseline subject information will be obtained in accordance with local regulations, including date of birth, age, sex (with child bearing status for females), race and ethnicity. In addition, relevant medical history (including CKD and ESRD history) and current medical conditions at screening, a full physical examination, vital signs and a pregnancy test (for females of child-bearing potential) will also be performed.

At Baseline/Transplantation information on the renal transplant procedure, recipient and donor transplant background, recipient and donor viral serology and recipient/donor HLA testing results will be recorded. Post-transplant, when all Inclusion/Exclusion criteria are met, the subject may be randomized. For randomization of subjects the IRT must be contacted, CNI and Donor status provided and the IRT will assign the treatment group. For all subjects regardless of randomization status the IRT and Screening Disposition CRF must be completed to

Protocol No. CRAD001A2433

document all consented subjects as either randomized or as screen failures and the reason for screen failure recorded in the CRF.

6.3 Treatment exposure and compliance

All pre-transplant immunosuppression administered, such as basiliximab, rATG and any other agents (CNI, MPA and/or corticosteroids) administered pre-randomization will be recorded on the Concomitant Medications CRF under the immunosuppressive category.

All post-randomization doses of everolimus, MPA, tacrolimus and cyclosporine administered during the course of the study will be recorded on the corresponding Dosage Administration Record CRF

For all these immunosuppressive drugs the start date, total dose, stop date and reason for dose administration or dose change are to be provided. If study drug is interrupted due to inability to tolerate oral medication and therapy via an NG tube is administered the non-study drug usage of the immunosuppressive should be recorded on the Concomitant Medications CRF under the immunosuppressive category.

Tacrolimus and cyclosporine trough levels will be determined locally and recorded on the relevant CRF. The local trough values will be used to adjust the tacrolimus and cyclosporine dosing. Post-discontinuation of study regimen, for subject remaining in study to Month 24, the CNI trough levels should be recorded on the appropriate local lab CRF.

Everolimus trough levels will be determined by the local Laboratory. However, for sponsor agreed centers where subject management is not possible using a local laboratory, the samples should be sent to the Designated Central laboratory. All local everolimus levels must be completed for all visits on the local everolimus CRF.

Other drugs administered prior to and continuing at start of study medication will be entered on the Concomitant medications CRF.

Compliance will be assessed by the investigator and/or study personnel at each visit and information provided by the subject. This information should be captured in the source document at each visit.

6.4 Efficacy

Treated Biopsy Proven Acute Rejection (tBPAR)

A treated BPAR is any condition where the subject received anti-rejection treatment and was histologically diagnosed as acute rejection (according to the Banff 2009 criteria, Appendix 6). Renal biopsies will be collected for all cases of suspected acute rejection.

Kidney allograft biopsy

For all suspected rejection episodes, regardless of initiation of anti-rejection treatment, an allograft biopsy must be performed within 48 hrs. Biopsies will be read by the local pathologist according to the updated Banff 2009 criteria (Appendix 6). The results of the biopsy read by the local pathologist will be listed on the Kidney Allograft Biopsy CRF. The results will be used for subject management for acute rejection. The local pathologist will remain blinded to

treatment. Any biopsies performed according to local practice (e.g. not for cause) should also be recorded.

Graft Loss

The allograft will be presumed to be lost on the day the subject starts dialysis and is not able to subsequently be removed from dialysis. If the subject undergoes allograft nephrectomy prior to starting permanent dialysis, then the day of nephrectomy is the day of graft loss. The reason for graft loss will be recorded on the Graft Loss CRF. This will be reported on the M12 or M24 study completion CRF with Graft Loss as the reason for study discontinuation and on the appropriate Dosage Administration Record CRF(s) if death occurs while on randomized treatment. Graft loss is considered a Serious Adverse Event and should be reported on the Adverse Event CRF (as serious) and the SAE reported to the local Novartis Drug Safety and Epidemiology Department local Novartis Drug Safety and Epidemiology (DS&E) Department within 24 hr.

Death

In the event of subject death, the SAE leading to Death should be reported to Novartis DS&E within 24 hr. The events leading to the death should be entered on the Adverse Event CRF and the death should be indicated on the appropriate Dosage Administration Record CRF(s) (if death occurs while on randomized treatment) and on the Study Completion CRF.

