Control regimen	Drug regimen used post-randomization as a comparator to evaluate comparative effects of the investigational drug (i.e. the combination of MPA and a CNI- either tacrolimus or cyclosporine)		
Enrollment	Point/time of subject entry into the study; the point at which informed consent must be obtained (i.e. prior to starting any of the procedures described in the protocol)		
Extension	Study period from Month 12 visit to completion of Month 24 visit regardless of treatment status (i.e. can be on or off randomized regimen)		
Investigational regimen	The investigational drug regimen tested in the study post-randomization (i.e. the combination of everolimus and a CNI- either tacrolimus or cyclosporine)		
Lost to follow-up	Those subjects whose status is unclear because they fail to appear for study visits without stating an intention to withdraw and cannot be contacted		
Subject Number	A number assigned to each subject who enrolls into the study		
Period	A distinct stage in the subjects' participation in the study, each period serves a purpose in the study as a whole		
Premature subject withdrawal	Point when the subject exits from the study prior to the planned completi of all assessments, synonymous with study discontinuation, not the sam as treatment discontinuation		
Primary Treatment Period	Study period from randomization to completion of Month 12 visit, regardless of treatment status (i.e. can be on or off randomized regimen)		
Screening period	Period from signing informed consent to successful completion of the transplant procedure		
Study Completion	Point at which the subject came in for a final evaluation visit at Month 24 or complete discontinuation from the study if prior to Month 24		
Study drug/ treatment	Any single drug or drug regimen administered to the subject as part of the required study procedures in any study period, includes everolimus, tacrolimus, cyclosporine, basiliximab, MPA and corticosteroids		
Treated biopsy proved acute rejection (tBPAR)	An acute rejection episode documented by histological evidence for which anti-rejection therapy (e.g. steroids, antibody or increase in study regimen immunosuppression) was given.		
Treatment discontinuation	Point when subject permanently stops taking study/investigational or control treatment drug/regimen for any reason, not the same as study discontinuation/premature subject withdrawal		

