Study Discontinuation	Point when subject permanently stops taking part in the study, also termed premature subject withdrawal, not the same as treatment discontinuation		
Variable	Information used in the data analysis; derived directly or indirectly from data collected using specified assessments at specified time points		

Protocol No. CRAD001A2433

Amendment 1

Amendment rationale

In response to the French Health Authorities (HA) request, the protocol is updated with the recent notifications for use of mycophenolate based on EMA's recommendation published on 23 Oct 2015, and the Dear Health Care Professional Letter (DHCPL) for CellCept that was distributed by Roche by 10-Nov-2015.

Mycophenolate (mycophenolate mofetil or mycophenolic acid) is a confirmed teratogen associated with an increased rate of spontaneous abortion and congenital malformation compared with other immunosuppressants. Therefore, investigators should ensure that female and male patients taking mycophenolate understand the risk of harm to the baby, the need for effective contraception, and the need to immediately consult responsible investigator if there is a possibility of pregnancy or a suspected gap of contraception.

Recommendations for female patients:

- Female patients sexually active should use two reliable methods of contraception simultaneously before starting and during therapy with mycophenolate, and for 6 weeks after stopping treatment following discontinuation of mycophenolate.
- Female patients should not donate blood during therapy with mycophenolate and at least 6 weeks following discontinuation of mycophenolate.

Recommendations for male patients:

- Male patients sexually active should use condom for sex during therapy with
 mycophenolate and at least 90 days following discontinuation of mycophenolate. Condom
 use applies for both reproductively competent and vasectomized male patients (due to the
 risks associated with the transfer of seminal fluid). In addition, female partners of male
 patients treated with mycophenolate are recommended to use highly effective
 contraception during treatment and for a total of 90 days after the last dose of
 mycophenolate.
- Male patients should not donate blood during therapy with mycophenolate and at least 6 weeks following discontinuation of mycophenolate.
- Male patients should not donate semen during therapy with mycophenolate and for 90 days following discontinuation of mycophenolate.

Changes to the protocol

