Subjects who discontinue their study treatment regimen should NOT be considered withdrawn from the study. Such subjects should remain in the study, if possible, and receive standard of care immunosuppression, according to local practice, until completing the study at Month 24. See Table 6-1 for the required assessments of these subjects after discontinuation of study regimen.

The status of every randomized subject must be recorded on Month 12 and/or Month 24 Study Phase Completion CRFs as either completing or discontinuing from the respective study period, with reason for discontinuation.

Possible reasons for discontinuation from the study are:

- Technical problems
- Subject/Guardian Decision
- Lost to follow-up
- Death
- **Graft Loss**
- Study terminated by sponsor
- Pregnancy

Subjects may voluntarily withdraw from the study for any reason at any time. They may be considered withdrawn if they state an intention to withdraw, fail to return for visits, or become lost to follow-up for any other reason.

If premature withdrawal occurs for any reason, the investigator must make every effort to determine the primary reason for a subject's premature withdrawal from the study and record this information on the Study Phase Completion CRF at Month 12 and/or Month 24 as applicable.

For subjects who are lost to follow-up (i.e. those subjects whose status is unclear because they fail to appear for study visits without stating an intention to withdraw), the investigator must show "due diligence" by documenting in the source documents steps taken to contact the subject, e.g. dates of telephone calls, registered letters, etc.

Subjects who are prematurely withdrawn from the study will not be replaced.

5.5.10 **Emergency breaking of treatment assignment**

Not applicable.

Study completion and post-study treatment 5.5.11

Subject who successfully complete 24 months on treatment may be eligible to participate in a separate observational extension study for a further three years. Subjects who are prematurely withdrawn from the study should be treated according to local standard of c are per investigator's judgment.

The study will be complete and ready for final analysis when the last active subject has completed their Month 24 visit.

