5.5.12 Early study termination

The study can be terminated at any time for any reason by Novartis. Should this be necessary, the subject should be seen as soon as possible and treated as for a prematurely withdrawn subject. The investigator may be informed of additional procedures to be followed in order to ensure that adequate consideration is given to the protection of the subject's interests. The investigator will be responsible for informing IRBs and/or ECs of the early termination of the trial.

6 Visit schedule and assessments

Table 6-1 lists all of the assessments and indicates with an "X" when the visits are to be performed. "A" indicates assessments only to be performed for subjects maintaining the study regimen (i.e. EVR+CNI or MPA+CNI). Subjects should be seen for all visits on the designated day or as close to it as possible.

The day of randomization will be considered to be study Day 1. Subjects will make scheduled study visits on Day 4, at the end of Weeks 1, 2 and 4 at the end of Months 2, 4, 6, 9, 12, 18 and 24. All randomized subjects are expected to continue in the study up to Month 24 regardless of being on or off randomized treatment status. Subjects who discontinue their randomized study treatment regimen should be treated according to standard of care immunosuppression and return for the assessments indicated by X in Table 6-1. If they refuse to return for these assessments or are unable to do so, every effort should be made to contact them or a knowledgeable informant by telephone to determine the subject and graft status.

At a minimum, subjects will be contacted for safety evaluations (SAEs) during the 30 days following the last study visit. Documentation of attempts to contact the subject should be recorded in the source documentation.

Assessment schedule- Study Treatment to Month 24 Table 6-1

Study Period	Screening ¹		Treatment to Month 12									Extension Treatment to Month 24		
Visit	SCR	BL ²	D4	W1	W2	W4	M2	M4	М6	М9	M12	M18	M2 4	
Visit Number	1	99	101	102	103	104	105	106	107	108	199	201	299	
Informed Consent ¹	Х													
Demographics	Х													
Inclusion/	X	Х												
Exclusion														
Medical History	Х												 	
Kidney Transplant Background Recipient/Donor		X												
Kidney Transplant Procedure		Х												
Viral serology ³ Recipient/Donor		Х												
Pregnancy test ⁴	Х								Х		Х	Х	Х	
IRT call	S	S												
Screening Disposition ¹		Х												

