### 2.1 Data Analysis General Information

The cut-off day is defined as the latest study day before and up to which data will be used in the analysis on an individual patient level. The cut-off date for 12-month analysis will be the day of Month 12 Visit (specifically, Date of Discontinuation/Study Phase Completion as recorded on the Month 12 Disposition eCRF) + 2 Weeks, but no later than Day 450 (upper limit of Month 12 analysis window). For the 24-month analysis, there will be no cut-off day. All data in the clinical database will be used for the analyses.

Data listings will include all data collected up to the cut-off date for the 12-month analysis, or all data recorded in the database for the 24-month analysis.

For summary tables and figures, the following rules will be applied unless otherwise indicated:

- Categorical data will be summarized by frequencies and percentages. Continuous data will be summarized by mean, median, standard deviation, minimum and maximum and the number of non-missing data points.
- All AE/Infection, notable events, CMV information, EBV information and other events of interest will be summarized based on all collected events with onset on or after the first day of study medication up to the cut-off date or seven days after last dose of study medication. For SAE/infection and death, all events will be summarized.
- All lab or vital sign tables will include data up to the cut-off date or two days after last dose of study medication (on-treatment analysis);

- Efficacy and renal function analyses will be primarily based on all available data including those after study medication discontinuation; as a sensitivity analysis they will include only data up to two days after last dose of study medication (on-treatment analysis). Patients will be censored for the time to event analyses if they do not have an event. For on-treatment analysis, the censoring day is two days after discontinuation of study medication or the last contact day, whichever is earlier; for analysis regardless of on-treatment or off-treatment, the censoring day is the last contact day.
- For post-baseline continuous values, for a given patient, if multiple numeric measurements for a given variable are reported within the same visit window (see the definition for visit windows in [Section 4.1](#)), the following rule will be applied:

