### 2.1.1.3 Last Contact Day

The last contact day for the 12-month analyses will be determined by screening the 12-month database and taking the maximum of any dates found post-randomization. If the maximum date is after the cut-off date for the 12-month analysis, use the cut-off day as the last contact day for the 12-month analysis.

The last contact day for the 24 months analyses corresponds to the last recorded date in the database (across all visit dates itself, all visit related assessment dates, other assessment dates, event dates (start and end), medication dates). It should be prior to or on the day of study completion and therefore dates of events which occur after study completion will not be considered.

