### 2.7.2.2 Endpoints without eGFR (MDRD4) < 50 mL/min/1.73m^2 as a Component

Based on FAS, for the composite efficacy failure (tBPAR, graft loss or death) at Month 24 and the composite endpoint of BPAR, graft loss or death at Month 12 and Month 24, Kaplan-Meier event rates will be estimated and compared between the everolimus plus reduced CNI and the MPA plus standard CNI arm. Similarly Kaplan-Meier event rates will be estimated and compared for AR, tAR, BPAR, tBPAR, tBPAR excluding grade IA rejections, AMR, graft loss, death, the composite endpoint of graft loss or death, and composite endpoint of tBPAR, graft loss, death, or loss to follow-up at Months 12 and 24. Kaplan-Meier event rate difference, 95% confidence interval and p-value for equality test will be provided. To assess time-to-event occurrence, Kaplan-Meier tables and plots will be produced with a log-rank test p-value for the above variables.

In addition, severity of tBPAR will be tabulated by treatment. The endpoint of tBPAR at Month 12 will be summarized on the FAS for the subgroups defined in [Section 2.2.1](#)

Forest plots of event rate differences for **all** efficacy endpoints specified in [Section 2.7.2](#) will be produced on the FAS.

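### The documents conflict on whether patients with graft loss stay in the study. On one reading the Kaplan-Meier death endpoint stops observing them, and its rate is too low if mortality rises after graft loss.

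*Protocol*

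**What the plan says.** **Text that takes these patients out of the study.**
- Protocol 6.4 has graft loss reported on the completion form "with Graft Loss as the reason for study discontinuation".
- In Protocol 5.5.9, the list headed "Possible reasons for discontinuation from the study are" contains graft loss and, as a separate item, death.
- The protocol glossary defines study discontinuation as "Point when subject permanently stops taking part in the study". It extends study completion to a final Month 24 visit "or complete discontinuation from the study if prior to Month 24".

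**Text that keeps them in.**
- Protocol 5.5.9 also lists graft loss among the reasons for stopping study treatment, and says that subjects who stop the regimen are not to be regarded as withdrawn.
- Protocol Section 6 states: "All randomized subjects are expected to continue in the study up to Month 24 regardless of being on or off randomized treatment status". Note 10 to Table 6-1 repeats this.
- Section 6 adds telephone contact, to establish subject and graft status, for subjects off the regimen who cannot or will not return.

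**What the SAP does with the dates.**
- In SAP 2.1 the individual 12-month cut-off is the "Date of Discontinuation/Study Phase Completion as recorded on the Month 12 Disposition eCRF) + 2 Weeks, but no later than Day 450". Event-free patients are censored at the last contact day.
- SAP 2.1.1.3 caps the 12-month last contact day at that cut-off. For the 24-month analysis it says that "dates of events which occur after study completion will not be considered".
- SAP 2.7.1 (item 5h) makes death alone an endpoint at Months 12 and 24, and SAP 2.7.2.2 says "Kaplan-Meier event rates will be estimated and compared for AR, tAR, BPAR, tBPAR, tBPAR excluding grade IA rejections, AMR, graft loss, death".

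**The concern.** Kaplan-Meier estimation assumes that a censored patient has the same later risk as the patients still under observation. A patient who has just lost the graft may well not. If graft loss ends observation, the censoring is tied to prognosis and the death rate describes little more than deaths with a functioning graft.

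Patient survival is a result that readers will look for when a reduced-CNI regimen is compared with a standard one. If graft loss differs by arm, the arm with more graft losses also has more unobserved deaths. A second problem is practical: sites can follow either set of instructions, so follow-up after graft loss may vary between centres.

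**Working it through.** **1. Plan's own figures.** The documents state no expected graft-loss or death rate, so there is no stated figure on this point to reproduce. Table 9-1 concerns the primary composite. Its non-inferiority power at 1020 per arm (above 99%) reproduces at 99.5% and does not depend on this issue.

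**2. Trace one patient under the leave-the-study reading.** The graft is lost and study discontinuation recorded at Month 3; death follows at Month 8.
- Month 12 analysis: the cut-off is the discontinuation date plus 2 weeks, so the death lies outside it and the patient is censored at about Month 3.5.
- Month 24 analysis: study completion is the discontinuation date. The last contact day cannot be later, so the death falls after censoring.
- Loss to follow-up (SAP 4.3.9): the patient is not counted as lost, because that definition excludes anyone who has had a graft loss.

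**3. Simple size by Month 24.** All rates are assumptions: 3% graft loss, 1.2 years of remaining follow-up on average, annual mortality after graft loss of 5% or 10%, and 3% deaths over two years otherwise (about 1.5% per year). The number randomised is 2040 (Protocol 9.7, 1020 per arm).
- Graft losses: 2040 × 0.03 = 61.2.
- Unobserved person-years: 61.2 × 1.2 = 73.4.
- Deaths in that time: 73.4 × 0.10 = 7.3, or 73.4 × 0.05 = 3.7.
- Deaths that Kaplan-Meier already credits to the censored patients: 73.4 × 0.015 = 1.1.
- Net shortfall: 7.3 − 1.1 = 6.2 deaths (6.2 / 2040 = 0.30 points), or 3.7 − 1.1 = 2.6 deaths (2.6 / 2040 = 0.13 points), over both arms.

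**4. Constant-hazard check.** This compares true cumulative death with the Kaplan-Meier rate when patients are censored at graft loss. HR is the hazard ratio for death after against before graft loss.

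| 12-month graft loss | 12-month death with function | HR | Short at Month 12 (points) | Short at Month 24 (points) |
|---|---|---|---|---|
| 3% | 1% | 1 | 0.00 | 0.00 |
| 3% | 1% | 3 | 0.03 | 0.12 |
| 3% | 1% | 10 | 0.13 | 0.50 |
| 3% | 3% | 3 | 0.09 | 0.33 |
| 3% | 3% | 10 | 0.37 | 1.29 |

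Over the whole grid (graft loss 1 to 5%, death 1 to 3%, HR 1 to 10) the shortfall is 0.00 to 0.61 points at Month 12 and 0.00 to 2.14 at Month 24. If deaths within 30 days of graft loss are counted, it is 0.00 to 0.51 and 0.00 to 1.93.

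**5. Between arms.** Assume 12-month graft loss of 5% against 3%, and 2% death with function in both arms. The true Month 24 difference in death is 0.15 points at HR 3 and 0.61 at HR 10. With censoring at graft loss, the Kaplan-Meier difference is 0.00 in both cases.

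**The case against.** A reader might infer that deaths after graft loss are simply not captured and that the reported death rates are understated. The documents support neither as a flat statement.

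**On capture.** The keep-in text can fairly be read as covering these patients. Graft loss is a listed reason for stopping treatment, such subjects are not withdrawn, and the telephone contact in Section 6 would then apply. Protocol 5.5.5 has dialysis and retransplantation recorded. Serious adverse events are collected to 30 days after the last visit, and follow-up of an existing one has no time limit (Protocol 7.2); graft loss is itself such an event. SAP 2.1 sets no cut-off day for the 24-month analysis and summarises all deaths in the safety tables. The SAP 2.1.1.3 sentence belongs to the definition of last contact, which otherwise takes the latest date in the database.

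This stands as evidence of conflict, and it rules out saying that the deaths are never recorded. It does not remove the problem. No text expressly requires vital status after graft loss, and recording a death does not put it into the Kaplan-Meier estimate if the last contact day stops at study completion. The 30-day window also catches little: in an example with 3% graft loss, 2% death and HR 5, about 16% of post-loss deaths by Month 12 and 8% by Month 24.

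**On direction.** Kaplan-Meier is biased low only if mortality is higher after graft loss. That is plausible, but the documents give no rate, and at HR 1 the bias is zero. A raw count of about 7 missed deaths would also overstate the effect, because roughly 1 is already credited.

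**On scope.** Death alone is an other secondary endpoint outside the testing hierarchy. The primary endpoint sets eGFR to zero after graft loss. The key secondary endpoint and the composite of graft loss or death count graft loss as an event. This objection stands in full.

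**Conclusion.** The concern holds as a conflict between passages with a conditional consequence. Protocol 6.4 and the study-discontinuation list in 5.5.9 point one way. The treatment-discontinuation list in 5.5.9, Section 6 and note 10 to Table 6-1 point the other. On the first reading, the SAP's date rules end observation for death at, or within two weeks of, the recorded study discontinuation.

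On the assumptions in step 3, the net shortfall by Month 24 is about 3 to 6 deaths over both arms (0.1 to 0.3 points), and it is smaller at Month 12. More extreme assumptions bring it to about 2 points at Month 24; equal mortality before and after graft loss brings it to zero. These figures also assume that the discontinuation date lies close to the graft-loss date and that no later follow-up enters the estimate. The confirmatory tests and the power figures are untouched, so this is a low-cost improvement and not a threat to the main conclusions.

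**What to change.** **Protocol.** Reconcile 5.5.9 (both lists), Section 6, note 10 to Table 6-1 and 6.4, so that they say one thing about participation after graft loss. State that vital status is obtained at Months 12 and 24 for every patient with graft loss. The telephone contact already in Section 6 is enough.

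**SAP.** Amend 2.1 and 2.1.1.3 so that, for the death endpoint, graft loss and the discontinuation date attached to it do not end observation. A patient would be followed to death or to the last date known alive, within the Month 12 or Month 24 analysis period. Both documents must change: with the protocol change alone, the deaths collected would still fall after the SAP's censoring date.

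**Cost.** Wording, plus at most two telephone contacts per patient with graft loss. At an assumed 3% that is about 61 patients and no more than 122 calls.
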